**Documenting the number of doses of ipilimumab and nivolumab combination and nivo monotherapy**
- 5) **Toxicity Form listing Grade 3, 4 SAEs and Grade 2-4 iRAEs on each subject (within 12 weeks of decision to stop treatment)**
- 6) **Follow-up Form** (every 3 months)
- 7) **Pathology** (submitted along with pathology specimens at end of patient treatment)
- 8) **Off-Treatment Form** (within 2 weeks after treatment terminates)

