## 6.0 **PATIENT MONITORING AND DATA SAFETY MONITORING**

As this is a tissue collection protocol in patients receiving standard of care therapy, patient management will occur through the standard operating procedures of the individual participating institution in general accordance with the FDA approved regimen.

Case Report forms documenting 1) patient demographic and tumor characteristics, 2) extent of treatment, 3) SAEs, 4) efficacy parameters and 5) specimen collection forms will be filled out for each patient.

The Principal Investigator and the Co-Investigators will discuss accrual, unusual toxicities and any other protocol issues including safety monitoring at their regular institution-based disease group meetings and on monthly investigator teleconferences. organized by the MRFBC.,

The Georgetown Lombardi Comprehensive Cancer Center will be responsible for the data and safety monitoring of this multi-site trial. As this study is an investigator initiated study utilizing FDA approved drugs for which the PI does not hold the IND it is

considered a moderate risk study which requires real-time monitoring by the PI and study team and semi-annual reviews by the LCCC Data and Safety Monitoring Committee (DSMC)

All Severe Adverse Events (SAEs) are required to be reported to the Multi-Site Coordinator Office at G-LCCC for review by the DSMC. (see below)

In addition, all SAEs are required to be reported to the local IRB per IRB policy. Based on SAEs, the IRB retains the authority to suspend further accrual pending more detailed reporting and/or modifications to further reduce risk and maximize the safety of participating patients.

Additionally, all SAEs will be reported to BMS Worldwide Safety using BMS SAE forms. Please refer to additional details in Appendix E. The sponsor/investigators are required to reconcile SAEs reported in the clinical database with SAE cases transmitted to BMS Global Pharmacovigilance (GPV&E); [REDACTED]. BMS requests this to be done quarterly and prior to the database lock or final data summary. A summary of the process for the sponsor/investigator is listed below:

- Sponsor/Investigator sends a request to BMS GPV&E for a “GPV&E reconciliation report”. Requests for reconciliation should be sent to [REDACTED]. The request should provide the BMS protocol ID, study title and PI, and sponsor/investigator protocol ID.

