- BMS will send a report back to the sponsor/investigator. The data elements listed on the GPV&E reconciliation report will contain information the investigator can use for individual case identification. Cases on the list from BMS GPV&E should be compared to the SAE cases in the clinical database.

If the sponsor/investigator determines a SAE case was not transmitted to BMS GPV&E, the case should be sent immediately to BMS

Progress on the trial and the toxicities experienced will be reviewed by the G-LCCC Data and Safety Monitoring Committee every 6 months from the time the first patient is enrolled on the study. Results of the DSMC meetings will be forwarded to the G-LCCC IRB with recommendations regarding need for study closure.

A written copy of the DSMC recommendations will be given to the trial PI and the Georgetown IRB. If the DSMC recommends a study change for patient safety or efficacy reasons the trial PI must act to implement the change as expeditiously as possible. In the unlikely event that the trial PI does not concur with the DSMC recommendations, then the G-LCCC Associate Director (AD) of Clinical Research must be informed of the reason for the disagreement. The trial PI, DSMC Chair, and the LCCC AD for Clinical Research will be responsible for reaching a mutually acceptable decision about the study and providing details of that decision to the IRB. Confidentiality must be preserved during these discussions. However, in some cases, relevant data may be shared with

other selected trial investigators and staff to seek advice to assist in reaching a mutually acceptable decision.

If a recommendation is made to change a trial for reasons other than patient safety or efficacy, the DSMC will provide an adequate rationale for its decision. If the DSMC recommends that the trial be closed for any reason, the recommendation will be reviewed by the Associate Director for Clinical Research at G-LCCC. Authority to close a trial for safety reasons lies with the IRB, with the above described input from DSMC and the AD for Clinical Research.

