## **7.0 EVALUATION AND MANAGEMENT OF TOXICITY**

As this is a tissue collection protocol in patients receiving standard of care therapy, formal documentation of physician evaluation and management of toxicity is not necessary. However, it is suggested that patients with life-threatening or persistent, severe toxic reactions to either checkpoint inhibitors receive no further treatment with either agent.

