### 10.3.3 Toxicity

The toxicity of nivolumab in combination with ipilimumab is well established in the melanoma patient population (9-11). As this treatment represents standard of care for this patient population, a formal analysis of toxicity is not considered as an endpoint for this study. As such, only the incidence of severe adverse events (immune related AEs) will be collected at the end of each patient's treatment course. A single page form will be provided to collect this summary

information. (see Section 7).

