### **Serious Adverse Event Collection and Reporting**

Following the subject's written consent to participate in the study, all SAEs, whether related or not related to study drug, must be collected, including those thought to be associated with protocol-specified procedures. All SAEs must be collected that occur within 100 days of discontinuation of dosing.

All SAEs must be collected that occur during the screening period. If applicable, SAEs must be collected that relate to any protocol-specified procedure (eg, a follow-up skin biopsy). The investigator should report any SAE that occurs after these time periods that is believed to be related to study drug or protocol-specified procedure.

SAEs, whether related or not related to study drug, and pregnancies must be reported to BMS within 24 hours. SAEs must be recorded on BMS or an approved form; pregnancies on a Pregnancy Surveillance Form.

**SAE Email Address:** [REDACTED]

**SAE Facsimile Number:** [REDACTED]

If only limited information is initially available, follow-up reports are required. (Note: Follow-up SAE reports should include the same investigator term(s) initially reported.)

If an ongoing SAE changes in its intensity or relationship to study drug or if new information becomes available, a follow-up SAE report should be sent within 24 hours to the BMS (or designee) using the same procedure used for transmitting the initial SAE report.

All SAEs should be followed to resolution or stabilization.

The Sponsor/Investigator will ensure that all SAEs in the clinical database are reported to BMS and any applicable health authority during the conduct of the study. This reconciliation will occur at least quarterly and be initiated by the sponsor/investigator. Sponsor/investigator will request a reconciliation report from: [REDACTED] During reconciliation, any events found to not be reported previously to BMS must be sent to [REDACTED]

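### The Toxicity Form (Section 11.0, item 5) leaves out fatal and lower-grade serious events, can fall due before the 100-day SAE window closes, and is the only listed record of non-serious irAEs, which therefore have no stated on-treatment route to the DSMC

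*Combined protocol and SAP*

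**What the plan says.** Section 11.0 lists eight forms for the electronic data capture system. Only one concerns toxicity, item 5: "Toxicity Form listing Grade 3, 4 SAEs and Grade 2-4 iRAEs on each subject (within 12 weeks of decision to stop treatment". No separate SAE form is listed, although Section 6.0 names SAEs among the case report form contents.

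Section 10.3.3 explains that toxicity is not an endpoint because the regimen is standard of care. It adds that "only the incidence of severe adverse events (immune related AEs) will be collected at the end of each" patient's treatment course, on a single-page form. Section 7.0 states that "formal documentation of physician evaluation and management of toxicity is not necessary".

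Other sections set up a separate SAE system. In Section 6.0, "All Severe Adverse Events (SAEs) are required to be reported to the Multi-Site Coordinator Office at G-LCCC for review by the DSMC". In Appendix E, "All SAEs must be collected that occur within 100 days of discontinuation of dosing", and "SAEs, whether related or not related to study drug, and pregnancies must be reported to BMS within 24 hours". Section 6.0 and Appendix E also require the SAEs in the clinical database to be reconciled with the company's list each quarter.

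Section 6.0 further says that "the toxicities experienced will be reviewed by the G-LCCC Data and Safety Monitoring Committee every 6 months", counted from the first enrolment. Section 8.0 has the date of death recorded for patients in follow-up.

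**The concern.** A toxicity form that stops at Grade 4 has no entry for the most important safety outcome of a checkpoint-inhibitor combination, a treatment-related death. The date of death is recorded elsewhere, but the protocol names no cause or attribution to go with it. If the final safety table is built from item 5 alone, fatal events and serious events of low grade would be missing from it, and so could events late in the 100-day window.

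Timing is a second problem. The DSMC is to look at toxicities every six months, but the form that holds non-serious irAEs is due only after a patient stops treatment. For a patient on long maintenance, several reviews could pass before those events are recorded.

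Finally, the sections describe different event sets: severe events (6.0), severe immune-related events only (10.3.3), Grade 3-4 SAEs plus Grade 2-4 irAEs (11.0), and all serious events (Appendix E). Severity and seriousness are different concepts, and Grade 2 irAEs are on the form although 10.3.3 limits collection to severe ones.

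**Working it through.** The plan gives no figure of its own for this point, so there is none to reproduce. The check compares which events each route covers, then does date arithmetic.

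**Inputs**
- Form content, and deadline of 12 weeks from the decision to stop: Section 11.0, item 5.
- SAE window of 100 days from the end of dosing, and 24-hour reporting to the company: Appendix E.
- SAE route to the DSMC and the six-monthly review: Section 6.0.
- Induction of 4 cycles every 3 weeks, then maintenance to at most 48 doses: Section 5.2. The maintenance interval is not given as a number. I assume 2 to 4 weeks, and that the 48 doses are maintenance doses.

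**Step 1: which events each route covers** (reading SAE as *serious*)

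| Event | Toxicity Form | SAE route to the DSMC |
|---|---|---|
| Serious, Grade 3-4 | Yes, after treatment | Yes |
| Fatal, Grade 5 | No | Yes |
| Serious, Grade 1-2, not immune-related | No | Yes |
| Non-serious irAE, Grade 2-4 | Yes, after treatment | No |

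The second and third rows are the gap in the summary. The fourth is the gap at the DSMC. If Section 6.0 were instead taken literally as *severe*, severe irAEs would gain a route to the DSMC, and serious events of low grade would lose theirs. That is a reason to settle the word.

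**Step 2: form deadline against the SAE window**

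12 weeks × 7 = 84 days, and 100 − 84 = 16 days. The two clocks start at different events. If the decision to stop comes L days after the last dose, the days not covered are max(0, 100 − 84 − L):
- L = 0: 16 days
- L = 7: 9 days
- L = 14: 2 days
- L ≥ 16: 0 days

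A form filed before its deadline, or a decision made before the last dose, widens the gap.

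**Step 3: how long before the form is due**

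Weeks from first dose = 12 (induction) + 48 × interval + 12 (deadline), for a patient who takes every maintenance dose:
- 2-week interval: 12 + 96 + 12 = 120 weeks, or 27.6 months. 27.6/6 = 4.6, so at least 4 reviews pass.
- 4-week interval: 12 + 192 + 12 = 216 weeks, or 49.7 months. 49.7/6 = 8.3, so at least 8 reviews pass.

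This is the longest case. A patient who stops at the end of induction has a form due by 12 + 12 = 24 weeks, or 5.5 months. Because reviews run from the first enrolment in the trial, at most one would fall in that time.

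**The case against.** The strongest reply is that the Toxicity Form is not the DSMC's source for SAEs. Section 6.0 sends all SAEs to the coordinating office for DSMC review without a grade limit, asks for real-time monitoring by the study team, and provides monthly investigator calls that cover unusual toxicities. Appendix E collects every SAE to day 100. Limited summary collection is also a deliberate choice, explained in Section 10.3.3 by the established toxicity of a standard regimen.

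Most of this stands, and it rules out three stronger readings that a reader might infer:
- *The DSMC would not see deaths or late SAEs.* The documents do not support this. Those events are SAEs and have their own route, although Section 6.0 sets no deadline for reports to the coordinating office.
- *The quarterly reconciliation cannot succeed because one section says severe and the other serious.* Section 6.0 uses the same acronym, sends all SAEs to the company and points to Appendix E, so *severe* reads as a slip in expanding it. Reconciliation also exists to find and repair mismatches.
- *About 40 patients would have missed events.* The background (Section 1.6) gives 55% Grade 3-4 treatment-related AEs, and 0.55 × 73 = 40. That counts patients with such events, many of which the form or the SAE route would hold. It does not count omissions.

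The reply does not cover the form's own contents, its cut-off, or non-serious irAEs during treatment. Appendix F has adverse events assessed at visits, but that schedule is only suggested. Section 11.0 has data reviewed continuously, but it lists no on-treatment form for these events.

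**Conclusion.** The point holds in three parts. First, as written, the end-of-treatment toxicity summary omits fatal events and lower-grade serious events. Second, its deadline can fall before the SAE window closes. The 16-day figure assumes that the decision falls on the last-dose day and that the form is filed on its due date; the shortfall is zero once the decision lags by 16 days or more. Third, non-serious Grade 2-4 irAEs have no stated on-treatment route to the DSMC. For a patient completing all 48 doses, at least 4 to 8 reviews could pass before the form is due, under the assumed interval of 2 to 4 weeks. For most patients the delay would be shorter, because treatment also ends at progression or intolerable toxicity.

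The number of events that would be lost cannot be estimated from the documents. The first two parts can be made good by merging the form with the SAE reports, but the plan does not say that the summary will be built that way. The consequence is confined to safety reporting: toxicity is not an endpoint, and the response-rate analysis does not depend on it.

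**What to change.** - Section 11.0, item 5: change the content to *all serious AEs (any grade, including Grade 5) and Grade 2-5 irAEs*.
- Finalise the form after the 100-day window closes, counted from the end of dosing as in Appendix E, and reconcile it with the SAE reports before the final safety summary.
- Enter irAEs to date in the data capture system before each six-monthly DSMC review.
- Section 6.0: expand SAE as *Serious Adverse Events*. Appendix E can be cited for the collection window but not for a definition, since it gives none.
- Section 10.3.3: name the same event set as item 5. Simply replacing *severe* with *serious* there would limit the sentence to serious immune-related events and contradict the form.

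There is no need to add every non-serious, non-immune Grade 3-4 event. The cost is one form revision, wording in three sections (6.0, 10.3.3 and 11.0), and modest interim data entry at sites. No treatment rule changes.

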## **12.0 PATIENT CONSENT AND PEER JUDGMENT**

All institutional, NCI, FDA, state, and Federal regulations concerning informed consent and peer judgment will be fulfilled.

## **13.0 PUBLICATION PLAN**

We anticipate that upon completion of this trial, the subsequent manuscript reporting the results will be published in the Journal of Clinical Oncology, or similar publication, within 12 months of the completion of the study analysis. Correlative science may be reported in a separate manuscript.

**PROTOCOL:**

Case No.: 00\_\_\_\_\_01 – GU LCCC

Subject Initials \_\_\_\_ (F,M,L)      Site #: \_\_\_\_\_

---

Contact Name: \_\_\_\_\_

Contact Phone: \_\_\_\_\_

Date of Shipment: \_\_\_\_\_

Shipping Conditions: \_\_\_\_\_  
(indicate dry ice, room temp, etc)

Sample Sent: \_\_\_\_\_  
(indicate total amount: i.e. one core biopsy)

Site of Biopsy: \_\_\_\_\_  
(indicate primary vs. metastasis and location)

Surgical Path Report Enclosed:      YES      NO

Formalin-Fixed Paraffin Embedded Biopsy: YES      NO

Frozen Tissue Biopsy (on dry ice):      YES      NO

Shipping Notes:  
Please fax form in advance to [name]  
Please include a copy of the form in the shipping container.

Specimen Received by: \_\_\_\_\_  
Date/Time Received: \_\_\_\_\_

**PROTOCOL:**

Case No.: 00\_\_\_\_\_01 – GU LCCC

Subject Initials \_\_\_\_ (F,M,L)      Site #: \_\_\_\_\_

---

Contact Name: \_\_\_\_\_

Contact Phone: \_\_\_\_\_

Date of Shipment: \_\_\_\_\_

Shipping Conditions: \_\_\_\_\_

(indicate dry ice, room temp, etc)

Date of Biopsy: \_\_\_\_\_

Sample Sent: \_\_\_\_\_

(indicate total amount: i.e. one core biopsy)

Site of Biopsy: \_\_\_\_\_

(indicate primary vs. metastasis and location)

Surgical Path Report Enclosed:      YES      NO

Formalin-Fixed Paraffin Embedded Biopsy: YES      NO

Frozen Tissue Biopsy (on dry ice):      YES      NO

**Shipping Notes:**

Please fax form in advance to [name]

Please include a copy of the form in the shipping container.

Specimen Received by: \_\_\_\_\_

Date/Time Received: \_\_\_\_\_

## **Appendix D** **RECIST v1.1 Response Criteria**

Definitions of measurable, non-measurable, target and non-target lesions and objective response criteria based on the REVISED (January, 2009) RECIST 1.1 criteria. This Appendix is for reference only. The complete RECIST 1.1 criteria are found at: [www.recist.com](http://www.recist.com).

### 1. Definition of Measurable and Non-Measurable Lesions

**Measurable disease.** Measurable lesions are defined as those that can be accurately measured in at least one dimension (longest diameter to be recorded) as  $\geq 20$  mm by chest x-ray, as  $\geq 10$  mm with CT scan, or  $\geq 10$  mm with calipers by clinical exam. All tumor measurements must be recorded in millimeters (or decimal fractions of centimeters).

Note: Tumor lesions that are situated in a previously irradiated area might or might not be considered measurable. If the investigator thinks it appropriate to include them, the conditions under which such lesions should be considered must be defined in the protocol.

**Malignant lymph nodes.** To be considered pathologically enlarged and measurable, a lymph node must be  $\geq 15$  mm in short axis when assessed by CT scan (CT scan slice thickness recommended to be no greater than 5 mm). At baseline and in follow-up, only the short axis will be measured and followed.

**Non-measurable disease.** All other lesions (or sites of disease), including small lesions (longest diameter  $<10$  mm or pathological lymph nodes with  $\geq 10$  to  $<15$  mm short axis), are considered non-measurable disease. Bone lesions, leptomeningeal disease, ascites, pleural/pericardial effusions, lymphangitis cutis/pneumonitis, inflammatory breast disease, and abdominal masses (not followed by CT or MRI), are considered as non-measurable.

Note: Cystic lesions that meet the criteria for radiographically defined simple cysts should not be considered as malignant lesions (neither measurable nor non-measurable) since they are, by definition, simple cysts.

‘Cystic lesions’ thought to represent cystic metastases can be considered as measurable lesions, if they meet the definition of measurability described above. However, if non-cystic lesions are present in the same patient, these are preferred for selection as target lesions.

**Target lesions.** All measurable lesions up to a maximum of 2 lesions per organ and 5 lesions in total, representative of all involved organs, should be identified as target lesions and recorded

and measured at baseline. Target lesions should be selected on the basis of their size (lesions with the longest diameter), be representative of all involved organs, but in addition should be those that lend themselves to reproducible repeated measurements. It may be the case that, on occasion, the largest lesion does not lend itself to reproducible measurement in which circumstance the next largest lesion which can be measured reproducibly should be selected. A sum of the diameters (longest for non-nodal lesions, short axis for nodal lesions) for all target lesions will be calculated and reported as the baseline sum diameters. If lymph nodes are to be included in the sum, then only the short axis is added into the sum. The baseline sum diameters will be used as reference to further characterize any objective tumor regression in the measurable dimension of the disease.

Non-target lesions. All other lesions (or sites of disease) including any measurable lesions over and above the 5 target lesions should be identified as non-target lesions and should also be recorded at baseline. Measurements of these lesions are not required, but the presence, absence, or in rare cases unequivocal progression of each should be noted throughout follow-up.

## 2. Methods of measurements

All measurements should be taken and recorded in metric notation using a ruler or calipers. All baseline evaluations should be performed as closely as possible to the beginning of treatment and never more than 4 weeks before the beginning of the treatment.

The same method of assessment and the same technique should be used to characterize each identified and reported lesion at baseline and during follow-up. Imaging-based evaluation is preferred to evaluation by clinical examination unless the lesion(s) being followed cannot be imaged but are assessable by clinical exam.

Clinical lesions: Clinical lesions will only be considered measurable when they are superficial (e.g., skin nodules and palpable lymph nodes) and  $\geq 10$  mm diameter as assessed using calipers (e.g., skin nodules). In the case of skin lesions, documentation by color photography, including a ruler to estimate the size of the lesion, is recommended.

Chest x-ray: Lesions on chest x-ray are acceptable as measurable lesions when they are clearly defined and surrounded by aerated lung. However, CT is preferable.

Conventional CT and MRI: This guideline has defined measurability of lesions on CT scan based on the assumption that CT slice thickness is 5 mm or less. If CT scans have slice thickness greater than 5 mm, the minimum size for a measurable lesion should be twice the slice thickness. MRI is also acceptable in certain situations (e.g. for body scans).

Use of MRI remains a complex issue. MRI has excellent contrast, spatial, and temporal resolution; however, there are many image acquisition variables involved in MRI, which greatly impact image quality, lesion conspicuity, and measurement. Furthermore, the availability of MRI is variable globally. As with CT, if an MRI is performed, the technical specifications of the scanning sequences used should be optimized for the evaluation of the type and site of disease.

Furthermore, as with CT, the modality used at follow-up should be the same as was used at baseline and the lesions should be measured/assessed on the same pulse sequence. It is beyond the scope of the RECIST guidelines to prescribe specific MRI pulse sequence parameters for all scanners, body parts, and diseases. Ideally, the same type of scanner should be used and the image acquisition protocol should be followed as closely as possible to prior scans. Body scans should be performed with breath-hold scanning techniques, if possible.

PET-CT: At present, the low dose or attenuation correction CT portion of a combined PET-CT is not always of optimal diagnostic CT quality for use with RECIST measurements. However, if the site can document that the CT performed as part of a PET-CT is of identical diagnostic quality to a diagnostic CT (with IV and oral contrast), then the CT portion of the PET-CT can be used for RECIST measurements and can be used interchangeably with conventional CT in accurately measuring cancer lesions over time. Note, however, that the PET portion of the CT introduces additional data which may bias an investigator if it is not routinely or serially performed.

Ultrasound: Ultrasound is not useful in assessment of lesion size and should not be used as a method of measurement. Ultrasound examinations cannot be reproduced in their entirety for independent review at a later date and, because they are operator dependent, it cannot be guaranteed that the same technique and measurements will be taken from one assessment to the next. If new lesions are identified by ultrasound in the course of the study, confirmation by CT or MRI is advised. If there is concern about radiation exposure at CT, MRI may be used instead of CT in selected instances.

Endoscopy, Laparoscopy: The utilization of these techniques for objective tumor evaluation is not advised. However, such techniques may be useful to confirm complete pathological response when biopsies are obtained or to determine relapse in trials where recurrence following complete response (CR) or surgical resection is an endpoint.

Tumor markers: Tumor markers alone cannot be used to assess response. If markers are initially above the upper normal limit, they must normalize for a patient to be considered in complete clinical response. Specific guidelines for both CA-125 response (in recurrent ovarian cancer) and PSA response (in recurrent prostate cancer) have been published [JNCI 96:487-488, 2004; J Clin Oncol 17, 3461-3467, 1999; J Clin Oncol 26:1148-1159, 2008]. In addition, the Gynecologic Cancer Intergroup has developed CA-125 progression criteria which are to be integrated with objective tumor assessment for use in first-line trials in ovarian cancer [JNCI 92:1534-1535, 2000].

Cytology, Histology: These techniques can be used to differentiate between partial responses (PR) and complete responses (CR) in rare cases (e.g., residual lesions in tumor types, such as germ cell tumors, where known residual benign tumors can remain).

The cytological confirmation of the neoplastic origin of any effusion that appears or worsens during treatment when the measurable tumor has met criteria for response or stable disease is

mandatory to differentiate between response or stable disease (an effusion may be a side effect of the treatment) and progressive disease.

**FDG-PET:** While FDG-PET response assessments need additional study, it is sometimes reasonable to incorporate the use of FDG-PET scanning to complement CT scanning in assessment of progression (particularly possible 'new' disease). New lesions on the basis of FDG-PET imaging can be identified according to the following algorithm:

- a. Negative FDG-PET at baseline, with a positive FDG-PET at follow-up is a sign of PD based on a new lesion.
- b. No FDG-PET at baseline and a positive FDG-PET at follow-up: If the positive FDG-PET at follow-up corresponds to a new site of disease confirmed by CT, this is PD. If the positive FDG-PET at follow-up is not confirmed as a new site of disease on CT, additional follow-up CT scans are needed to determine if there is truly progression occurring at that site (if so, the date of PD will be the date of the initial abnormal FDG-PET scan). If the positive FDG-PET at follow-up corresponds to a pre-existing site of disease on CT that is not progressing on the basis of the anatomic images, this is not PD.
- c. FDG-PET may be used to upgrade a response to a CR in a manner similar to a biopsy in cases where a residual radiographic abnormality is thought to represent fibrosis or scarring. The use of FDG-PET in this circumstance should be prospectively described in the protocol and supported by disease-specific medical literature for the indication. However, it must be acknowledged that both approaches may lead to false positive CR due to limitations of FDG-PET and biopsy resolution/sensitivity.

Note: A 'positive' FDG-PET scan lesion means one which is FDG avid with an uptake greater than twice that of the surrounding tissue on the attenuation corrected image.

